4. DESCRIPTION OF PROCEDURES

A) PCP Education and Randomization:

After obtaining PCP informed consent and prior to patient recruitment, a one hour educational session will be held for PCPs participating in the study. The purpose of this session is to provide education to PCPs about COPD, asthma, spirometry, and GOLD and GINA guidelines (GOLD=Global Initiative for Chronic Obstructive Lung Disease, GINA=Global Initiative for Asthma). The educational session will provide continuing medical education credit to those who attend. The learning objectives will be the following: 1) Review COPD and asthma disease definition, presentation, diagnosis and testing including spirometry, 2) be familiar with the GOLD and GINA guidelines and recommendations for therapy.

PCPs who consented to participate in the study and completed the education session will be randomized to have their patients who meet the study criteria receive the intervention or usual care.

B) Patient subject- Intervention:

On the day of the outpatient visit, subjects will be advised to arrive 90 minutes prior to their clinic visit in the same building as the clinic site or the CRC (Clinical Research Center at UIC). The following information will be collected and procedures will be performed:

1. Subject demographic and contact information
2. Co-morbid conditions
3. Smoking history
4. Medication history from patient and also from pharmacy used by subjects
5. A respiratory exacerbation history in the past year
6. Modified Medical Research Counsel (mMRC) dyspnea scale and COPD Assessment Test
7. Quality of life measures
8. Pre and post-bronchodilator (BD) spirometry
9. De-Escalation Spirometry Screener for patients de-escalating based on spirometry (See Based on spirometry findings)
10. De-Escalation Phone Script

Based on spirometry findings:

1. If the spirometry findings are consistent with COPD and/or asthma, the following will be provided to the provider and patient to have available during the clinic visit: a letter summarizing the interpretation of the findings using GOLD/GINA criteria with recommendations for initial guideline driven therapy based on GOLD/GINA guidelines. Subjects will be managed by their PCP thereafter.

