2. If the spirometry findings are normal, with approval from the PCP, will de-escalate respiratory medication therapy via a stepwise process and schedule patient back for a repeat pre and post bronchodilator spirometry within 1-2 weeks at the same time and place as the PCP clinic session or the CRC (Clinical Research Center at UIC). Again with the PCP approval, this

deescalation and repeat spirometry can occur in 1-2 week intervals until all maintenance medications are discontinued as long as the pre and post spirometry continues to be normal. After each visit, the following will be provided to the provider and patient: a letter summarizing the interpretation of the findings using GOLD/GINA criteria with recommendations for initial guideline driven therapy based on GOLD/GINA guidelines, if appropriate. Subjects will be managed by their PCP thereafter.

3. All spirometry test results and the subject's assessment at the time of the test will be uploaded into the subject's electronic health record for future reference.

C) Patient subject- Usual Care:

On the day of the outpatient visit, subjects will be advised to arrive 60 minutes prior to their clinic visit in the same building as the clinic site or the CRC (Clinical Research Center). The following will be performed.

1. Subject demographic and contact information
2. Co-morbid conditions
3. Smoking history
4. Medication history from patient and also from pharmacy used by subjects
5. A respiratory exacerbation history in the past year
6. Modified Medical Research Counsel (mMRC) dyspnea scale and COPD assessment test
7. Quality of life measures

Subjects will be advised to go to their clinics and be managed by their PCP thereafter.

At the end of the 1 year followup, the patient will be scheduled for a pre and post BD spirometry and undergo the same spirometry protocol (de-escalation protocol) as the intervention group.

Based on spirometry findings:

1. If the spirometry findings are consistent with COPD and/or asthma, the following will be provided to the provider and patient: a letter summarizing the interpretation of the findings using GOLD/GINA criteria with recommendations for initial guideline driven therapy based on GOLD/GINA guidelines. Subjects will be managed by their PCP thereafter.

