For **Aim 3: Costs**: The intervention costs for the study include the cost of the spirometry test, the time of the CHW/health promoter, and time of pulmonologist to provide periodic oversight of spirometry validity. In addition to estimating the costs associated with the intervention it will be important to measure the healthcare utilization for participants included in the study. It is possible that the intervention leads to use of other healthcare resources, particularly if the patient is determined to be free of respiratory disease. Therefore, we will measure both respiratory-related and overall healthcare costs. To measure these costs, we will determine overall healthcare utilization and apply unit costs to each of the events. Using chart reviews, we will examine healthcare utilization during the follow-up period. We will categorize healthcare utilization into either respiratory-related or all other healthcare use. We will apply standardized prices to each of the utilization components to estimate the overall and respiratory-related healthcare resource use during the study period. The standardize prices will be based on either the National Committee for Quality Assurance standardize price list for their relative resource use measure or Medicare reimbursement rates. For medications, we will rely on average wholesale price of medications to assign an average price to each of the COPD and asthma-related medications.

Cost-Effectiveness: The secondary outcome measures included in the study will be used to estimate the effectiveness to be used in the cost-utility analysis. We will use responses to the EQ5D to estimate patient utility and use that in calculation of quality-adjusted life-years (QALY). The area under the curve will be compared between the two groups and the difference will be the incremental effect used in the cost-utility analysis.

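### Aim 3 values respiratory drugs at average wholesale price but services at standardized or Medicare prices, so the ICER numerator mixes two price bases and no sensitivity analysis tests the choice

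*Combined protocol and SAP*

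**What the plan says.** Section 5, Aim 3: Costs, contains three costing rules.

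- **Services.** Unit prices come from one of two sources, the NCQA "standardize price list for their relative resource use measure or Medicare reimbursement rates". The choice between them is left open.
- **Drugs.** "we will rely on average wholesale price of medications to assign an average price to each of the COPD and asthma-related medications". The rule is not limited by arm or direction. It covers respiratory drugs started as well as stopped, in both groups.
- **Program.** "The intervention costs for the study include the cost of the spirometry test, the time of the CHW/health promoter, and time of pulmonologist", the last of these for periodic checks on test validity.

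The cost-utility paragraph takes as numerator the between-group difference in program cost and respiratory-related use, and divides by the QALY difference. Uncertainty comes from bootstrap limits and acceptability curves. The one cost sensitivity analysis stated replaces respiratory-related use with overall use.

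Section 4 B) describes the program. After a normal result the plan is to "schedule patient back for a repeat pre and post bronchodilator spirometry within 1-2 weeks" and, with PCP approval, "deescalation and repeat spirometry can occur in 1-2 week intervals until all maintenance medications are discontinued". The procedures also list a "De-Escalation Spirometry Screener for patients de-escalating based on spirometry" and a phone script, and the provider and patient receive "a letter summarizing the interpretation of the findings using GOLD/GINA criteria with recommendations for initial guideline driven therapy".

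**The concern.** Section 2 requires every participant to be using a maintenance respiratory drug. The pathway can withdraw all such drugs in patients with normal spirometry, and its letters can prompt treatment in the others. Drug spending is therefore likely to be a main driver of the numerator. If that component is valued at a list price and the rest on a payer or standardized basis, the sum is not the cost seen by any single payer, and comparing the ICER with a willingness-to-pay threshold becomes hard to interpret.

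The planned uncertainty analysis would not reveal this. The bootstrap, as described, reflects variation between patients, and nothing says that unit prices are varied. The confidence limits and acceptability curves would carry the pricing choice forward unseen.

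A smaller matter is that the program cost list does not say how the repeat-visit pathway is counted.

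**Working it through.** The documents give no unit price, drug cost or projected ICER, so there is no figure to reproduce. The arithmetic below is illustrative, and its assumptions are marked.

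**1. Effect of the mixed price basis.** Write the numerator as ΔP + ΔS + ΔD (program, services, drugs), with ΔD valued at wholesale price. Let r be price paid divided by wholesale price, taken as the same for all drugs (assumption).

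- On a payer basis the drug term is r × ΔD. The plan's numerator differs from this by (1 − r) × ΔD, and the ICER by (1 − r) × ΔD / ΔQALY.
- With r = 0.50 to 0.85 (assumption), each $100 of counted difference is worth $50 to $85. The overstatement factor is 1/0.85 = 1.18 to 1/0.50 = 2.00.
- The sign of the distortion is the sign of ΔD.

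**2. Can the sign of ΔD be settled?** Inputs:

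- p = 30–50% with normal spirometry (the misdiagnosis range in Background and Significance, used as a proxy)
- a = 50–100% of these approved for de-escalation by the PCP (assumption)
- u = share of the remaining patients whose therapy is stepped up (unknown)
- saving per de-escalated patient = added cost per stepped-up patient = 100 units at price paid (assumption)

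Net drug change = −(p × a × 100) + (1 − p) × u × 100. It is zero at u = p × a / (1 − p):

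| p | a | break-even u |
|---|---|---|
| 0.3 | 0.5 | 0.15/0.7 = 21% |
| 0.3 | 1.0 | 0.30/0.7 = 43% |
| 0.5 | 0.5 | 0.25/0.5 = 50% |
| 0.5 | 1.0 | 0.50/0.5 = 100% |

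Two cases with p = 0.3 and a = 1:

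- u = 0.25: −30 + 17.5 = −12.5 at price paid. At wholesale price this reads −12.5/0.85 = −14.7 to −12.5/0.50 = −25.0, a saving overstated.
- u = 0.50: −30 + 35 = +5.0 at price paid. At wholesale price this reads +5.0/0.85 = +5.9 to +5.0/0.50 = +10.0, an added cost overstated.

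The same rule exaggerates either result, and the documents do not fix u.

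**3. Program sessions.** Mean sessions per intervention patient = 1 + p × a × k, with k = 1 to 3 repeats (assumption).

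- Low: 1 + 0.3 × 0.5 × 1 = 1.15. High: 1 + 0.5 × 1 × 3 = 2.5.
- If only one test per patient is priced, 0.15/1.15 = 13% to 1.5/2.5 = 60% of sessions go uncosted.
- If every test is priced, 0% do.

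These are shares of sessions, not of program cost or of the ICER.

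**4. Where a repeat test may land.** Study spirometry is uploaded to the health record (Section 4 B), utilization for costing comes from chart review (Section 5), and those reviews collect other pulmonary function tests (Section 4 E). A repeat test found there and classed as respiratory-related enters the same numerator. Counted under both labels, it overstates cost. Counted under neither, it understates cost.

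**The case against.** A reader might infer something stronger: that Aim 3 understates the program's cost and overstates its savings, so that the ICER leans towards cost-effectiveness. The documents do not support this.

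- The cost list says that costs *include* certain items, so it need not be exhaustive. The spirometry test can be read as a category covering every session, and promoter time can cover phone contacts and letters.
- As step 4 shows, a repeat test picked up in chart review may already be in the numerator, or may be counted twice.
- Wholesale price applies to all respiratory drugs in both arms, not only to those withdrawn. Starting guideline therapy is a secondary outcome, so net drug cost may rise.
- PCP education is neutral between arms, because "PCPs who consented to participate in the study and completed the education session will be randomized".

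It can also be said that a single published drug price for both arms is simple and reproducible, that the documents do not show how far wholesale price lies above price paid, and that the overall-use analysis reduces reliance on the respiratory label.

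All of this stands against a claim of direction. It does not answer the price-basis point. A common list price still scales the between-arm drug difference, and switching to overall use leaves respiratory drugs at the same price.

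**Conclusion.** The concern holds as a mixed price basis in the ICER numerator, with no planned analysis that would expose it. If price paid is 50–85% of wholesale price, the net drug-cost difference is overstated by a factor of 1.18 to 2.00, in whichever direction it runs. That rests on an assumed ratio, common to all drugs. If the ratio differs between drugs stopped and drugs started, the distortion is no longer a simple scaling. The effect on the ICER itself cannot be sized, because the documents give no drug cost, program cost or QALY difference.

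The content of the program cost list is a point for clarification only. No under-costing is demonstrated. The change is worth making before the economic analysis; it does not touch the clinical outcomes.

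**What to change.** In Section 5, Aim 3:

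1. Name one price source for services instead of leaving two open.
2. In the base case, value drugs on the same payer basis as services, and name the drug price source in advance. Report average wholesale price as a sensitivity analysis, with its own ICER, bootstrap limits and acceptability curve.
3. As a clarification, state that intervention cost covers every study spirometry session (the baseline visit and repeat de-escalation visits) and PCP time for de-escalation decisions. State also that study spirometry found in chart review is counted only once.

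The cost is some SAP wording, one more set of drug prices and a rerun of the cost-utility analysis. Counting sessions needs study visit records, which should exist because each additional spirometry visit is paid at $50 (Section 4 F), although the documents do not describe a log. The ICER may come out less favourable.

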- 2. List of current respiratory medications from subject's pharmacy and verification with patient
- 3. Use of diagnostic testing: ECG, echocardiograms, CT/CXR, stress testing, cardiac catheterization, other pulmonary function tests
- 4. Any ED visits or hospitalizations or acute outpatient care visit and associated cause.
- 5. Healthcare utilization outside of U of I system (e.g. testing such as spirometry, ED and hospitalizations) if available through scanned records

3) All subjects will be contacted every 3 months after the initial visit via telephone (T_1 , T_2 , T_3 , T_4) up to one year; or they will be given the option to complete in person based on subject's convenience, for example they have a doctor appointment near time of study follow-up. These phone calls will be used to obtain follow-up data since last study contact. A reminder post-card will be mailed to the subjects a month before the next telephone contact.

- 1. Change in type of health insurance or self-pay

2. List of current respiratory medications from subject's pharmacy and verification with patient
3. Use of diagnostic testing: ECG, echocardiograms, CT/CXR, stress testing, cardiac catheterization, other pulmonary function tests
4. Any ED visits or hospitalizations or acute outpatient care visit and associated cause.
5. Healthcare utilization outside of U of I system (e.g. testing such as ancillary testing, ED and hospitalizations)
6. mMRC
7. A respiratory exacerbation history
8. EQ-5D 5L +B Bolt-on
9. SF-36 short form (at 3, 6 and 12 months)
10. Social support survey (at 6 months and 12 months)

F) Monetary compensation of subjects

1. PCP compensation:

UI Health and MSHC PCPs will receive \$95 in cash after completion of the education session. For CCHHS PCPs, the Division or Department will receive a total of \$95 per participant to be part of the divisional fund to be used by the PCP at their discretion as allowed by their institution.

2. Patient subject compensation:

Baseline visit (Vo):

Same for Intervention and usual care groups: Subjects will be provided \$75 in cash for completing the initial study visit.

Telephone contact (T₁-T₃):

Same for Intervention and usual care groups. Subjects who choose to complete the follow-up in person or via telephone will receive \$20 in cash at the time of the visit or at a later specified time that is convenient for the subject.

Final contact (T₄):

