Cost-utility analyses: We will evaluate the cost-utility of the intervention compared to usual care over the study period using recommended methods for cost-effectiveness analysis.⁷⁴ To compare the cost-effectiveness of the intervention to usual care, the findings are summarized into a ratio that provides the results in terms of the costs per unit of effect. We will calculate the difference in intervention costs and respiratory-related healthcare resource use between groups to determine the numerator of the ratio and the denominator will be the difference in QALYs in the cost-utility analysis. These incremental cost-effectiveness ratios (ICERs) will represent the cost per gain in QALYs for the intervention compared to standard care. As part of the cost-utility analysis we will evaluate the uncertainty associated with the ICERs. We will use bootstrapping

methods to generate confidence limits for the ICERs.^{75,76} We will display the results graphically on a cost-effectiveness plane and generate cost-effectiveness acceptability curves for the intervention compared to usual care.^{77,78} Cost-effectiveness acceptability curves display the probability of the intervention being cost-effective given various threshold values.⁷⁸ Thus decision-makers can identify a threshold value appropriate for their setting and determine the probability that the intervention will be cost-effective. We will also conduct sensitivity analyses that use the measure of overall healthcare utilization in calculation of the costs, as there may not be perfect specificity in identifying respiratory-related costs during the follow-up assessments and the intervention may lead to differences in non-respiratory costs.

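### The overall-cost measure in Aim 3, and the sensitivity analysis built on it, leave out non-respiratory drugs, which are neither recorded at follow-up nor priced

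*Combined protocol and SAP*

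**What the plan says.** Section 5 (Statistical Analyses, Aim 3: Costs) gives the reason for a wide cost measure: "It is possible that the intervention leads to use of other healthcare resources, particularly if the patient is determined to be free of respiratory disease". It then commits to it: "Therefore, we will measure both respiratory-related and overall healthcare costs". The data source is stated as "Using chart reviews, we will examine healthcare utilization during the follow-up period". Drugs have their own rule: average wholesale prices are used to "assign an average price to each of the COPD and asthma-related medications". No price source is named for any other drug.

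Under Cost-utility analyses in the same section, the main ratio takes intervention cost plus respiratory-related resource use as its numerator. Overall utilization enters as a sensitivity analysis, partly because "the intervention may lead to differences in non-respiratory costs".

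Section 4 E (Data collection and follow-up) lists what is collected every three months. The chart-review list and the telephone-contact list each have one drug item, in the same words: "List of current respiratory medications from subject's pharmacy and verification with patient". A drug item not restricted to respiratory medication, "Medication history from patient and also from pharmacy used by subjects", appears only among the first-visit items for each arm (sections 4 B and 4 C).

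**The concern.** The plan foresees that the intervention may move care from respiratory to other resources, and it relies on the overall-cost analysis to show this. Drug treatment is one form such a move could take: Background and Significance names cardiovascular disease and obesity as other sources of dyspnea and refers to missed diagnoses of other chronic conditions. If a patient's breathlessness is re-attributed and a drug is started for the new diagnosis, its cost does not enter any cost measure in the plan. The matching reduction in inhalers does.

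At stake is whether the sensitivity analysis can do its job. A reader who sees similar ratios from the respiratory-only and the overall analysis would take this as evidence that non-respiratory costs do not matter, when a whole category of them was never measured.

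**Working it through.** The plan states no cost, price or ratio, so there is no figure to reproduce. The check compares what is recorded with what is priced.

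| Cost component | Recorded at follow-up (4 E, items 2 and 3) | Price source (section 5, Aim 3) |
|---|---|---|
| Respiratory drugs | Yes, in both lists | Average wholesale price |
| Diagnostic tests | Yes | Standardized price list or Medicare rates |
| ED visits, hospitalizations, acute outpatient visits | Yes | Standardized price list or Medicare rates |
| Non-respiratory drugs | No | None stated |

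The last row fails on both counts. The general medication history cannot fill it, because it is taken at the first visit, before any drug could be started in response to study spirometry.

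**Does the gap fall evenly on the arms?** The recording rule is the same in both, so any bias must come from a difference in non-respiratory drug use.

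- In the intervention arm, normal spirometry leads, with PCP approval, to stepwise reduction "until all maintenance medications are discontinued as long as the pre and post spirometry continues to be normal" (section 4 B). These changes are recorded and priced.
- In usual care, study spirometry comes only at the end of the one-year follow-up (section 4 C).
- Re-diagnosis prompted by study spirometry during follow-up therefore occurs only in the intervention arm. Whether it raises, leaves or lowers non-respiratory drug use is not stated anywhere.

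**Illustration of size.** Only the first input comes from the documents.

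- m = share misdiagnosed: 0.30 to 0.50 (Background and Significance)
- f = net share of those patients starting a non-respiratory drug, relative to usual care: -0.10, 0, or 0.25 to 0.50 (assumed)
- c = yearly cost of that drug: $100 to $2,000 (assumed)
- ΔQ = QALY gain: 0.01 or 0.03 (assumed)

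Omitted cost per intervention patient = m × f × c. Shift in the sensitivity ratio = omitted cost / ΔQ. A positive value means that the reported overall cost, and so the ratio, is too low for REDEFINE.

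| f | Omitted cost per patient | Shift at ΔQ = 0.01 | Shift at ΔQ = 0.03 |
|---|---|---|---|
| 0.25 to 0.50 | 0.30 × 0.25 × $100 = $7.50 to 0.50 × 0.50 × $2,000 = $500 | $750 to $50,000 per QALY | $250 to about $16,700 per QALY |
| 0 | $0 | $0 | $0 |
| -0.10 | 0.30 × (-0.10) × $100 = -$3 to 0.50 × (-0.10) × $2,000 = -$100 | -$300 to -$10,000 per QALY | -$100 to about -$3,300 per QALY |

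The value of m is probably generous. The background also describes confusion between asthma and COPD, and such patients still have respiratory disease.

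**The case against.** The strongest reply is that overall utilization, taken at its word, already includes every drug, and that staff reviewing the chart can see them. This does not hold. The general wording states an intent, but the one drug-pricing sentence and both collection lists are specific, and none of them carries the intent out.

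Other objections do stand.

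- A reader might infer that the cost comparison is biased in favour of REDEFINE. The documents do not establish this. The plan says only that other resource use is possible. It also gives a route to the opposite sign: the background links unnecessary respiratory drugs to pneumonia and cardiovascular events, so stopping them could avoid other drug costs.
- A net saving on inhalers is not assured either. De-escalation needs normal spirometry and PCP approval, while patients with confirmed disease receive guideline recommendations that may add respiratory drugs, and these would be priced.
- The sensitivity analysis is incomplete, not empty. It still captures non-respiratory tests, ED visits, hospitalizations and acute visits.
- Routine non-acute visits are also missing from the follow-up lists, so adding drugs alone would not make the measure fully overall.

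**Conclusion.** The gap is real: the overall cost does not contain overall drug cost, and nothing else in the document supplies it. It affects the overall-cost measure and the sensitivity ratio that uses it.

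A reader might go further and conclude that the main cost-effectiveness result of Aim 3 is compromised. It is not, on this ground: its numerator is confined by design to intervention and respiratory-related cost, so non-respiratory drugs were never part of it. What is weakened is the check on that choice.

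The finding itself rests on the text alone. Its direction is conditional: it favours REDEFINE only if re-diagnosis produces a net rise in non-respiratory drug use. Its size is unknown. The range of -$100 to $500 per intervention patient depends on assumed uptake and prices, and the per-QALY shifts depend also on an assumed QALY gain; they show only that the effect could be negligible or material.

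**What to change.** In section 4 E, change the drug item in both quarterly lists to the full current medication list, in both arms, from the pharmacy source already queried. In section 5 (Aim 3: Costs), price all medications on the same average-wholesale-price basis and include them in the overall cost. Keep COPD and asthma drugs alone for the respiratory-related cost, so the main ratio does not change.

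This needs no new visit or procedure, but it is not free: about 500 patients × 4 quarterly time points = 2,000 fuller drug lists to enter and price, with both chart review and patient contact feeding each one.

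Where this cannot be done, for example for follow-up already completed, rename the measure *overall cost excluding non-respiratory medication*, state that it may favour the intervention, and do not present it as a full check on non-respiratory costs. Any dollar range reported for the missing part should be labelled as assumed and should include zero and negative values.
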